5.5.2 Doses and treatment regimens

At Visit 2 (randomisation) eligible patients will be randomly assigned to one of three treatment arms, AZD6140 45mg, 90mg twice daily or clopidogrel 75mg once daily, taken orally.

Randomisation and treatment pack assignment will be managed via the IWRS and the first dose of study medication should be taken directly after randomisation at Visit 2. Subsequent maintenance doses should be taken morning and evening, at approximately 12-hourly intervals, for the remainder of the treatment period.

Study medication should be swallowed whole with water. Study medication should not be altered (eg, crushed, put in another vehicle) and should not be given by nasogastric tube or other routes.

5.5.3 Concomitant ASA

In addition to randomised study medication all patients should be treated with concomitant ASA 81 to 100mg daily for at least 2 weeks prior to Visit2 and during the treatment period according to local practice. This medication will be open label and obtained locally.

5.5.4 Labelling

Labelling of the investigational products will be carried out by AstraZeneca or a Contract Research Organization in accordance with current Good Manufacturing Practice (GMP). The labels will be translated into local languages and in accordance with local regulations for each participating country. The labels will fulfil GMP Annex 13 requirements and/or local regulatory guideline.

All investigational products will be labelled. Information from the labels will be transferred to suitable forms in the Investigator's Study File (ISF).

5.5.5 Storage

All study drugs should be kept in a secure place under appropriate storage conditions. The investigational product label on the bottle specifies the appropriate storage.

For Japan, replace the above paragraph with the paragraph below

A description of the appropriate storage conditions is specified in the document 'Procedure of storage conditions for investigational product'.

5.6 Concomitant and post-study treatment(s)

All medications (defined as ASA and ongoing prescriptions) will be recorded from 14 days prior to Visit2 and throughout the study until the follow-up visit.

5.6.1 Parenteral anticoagulants

Treatment with approved parenteral anticoagulants (eg. unfractionated heparin (UFH), LMWH, bivalirudin, fondaparinux) is not allowed during the study. If treatment with parenteral anticoagulant drugs is considered essential during the study, study medication must be discontinued.

5.6.2 Oral anticoagulants

Concomitant treatment with anticoagulant drugs is not allowed during the study. If treatment with anticoagulant drugs is considered essential during the study, study medication must be discontinued.

5.6.3 Oral antiplatelet therapies and NSAIDs

ASA: All patients should take open label ASA at a dose of 81 to 100mg once daily throughout the study. ASA for pain relief should where possible be discouraged and paracetamol (acetaminophen) given.

Clopidogrel sulphate and Ticlopidine: Patients who are currently taking clopidogrel are not eligible to enter the study.

Dipyridamole and cilostazol: Patients who are currently taking any of these drugs are eligible to enter the study but treatment must be discontinued at least 14 days prior to Visit 2. Further dosing of any of these drugs in addition to study medication is not allowed during the study.

Other oral antiplatelets: Clinical experience with other drugs with antiplatelet effect (e.g., non-steroidal anti-inflammatory drugs (NSAIDs)) in combination with AZD6140 is limited at this time. Treatment with these types of drug (including NSAIDs) is allowed pre-study and/or during the study, at the investigator's discretion. However, chronic daily dosing with non-selective NSAIDs (eg, patient with rheumatoid arthritis) may increase the potential for GI bleeding so either alternative therapy or concomitant acid suppression is recommended. Treatment with selective cyclooxygenase-2 inhibitors is permitted, although use is cautioned.

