4. SUBJECT SELECTION CRITERIA

Investigator(s) should keep a record, the subject screening log, of subjects who entered pre-study screening.

Each subject should meet all of the inclusion criteria and none of the exclusion criteria for this study. Under no circumstances can there be exceptions to this rule.

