4.2 Exclusion criteria

Subjects should not enter the study if any of the following exclusion criteria are fulfilled:

1. ACS, transient ischaemic attack (TIA) or stroke within the 3 months prior to Visit 2.
2. Known concurrent disease of Stroke or TIA with atrial fibrillation
3. Concomitant antiplatelet therapy other than ASA within the 14 days prior to Visit 2.
4. Full dual antiplatelet treatment required according to clinical judgment
5. Fibrinolytic therapy within 2 weeks prior to Visit 2 or is planned to be administered for any conditions during the study.
6. Patients who implanted Drug-eluting stent
7. Any percutaneous intervention (eg, coronary, peripheral or cerebral), carotid endoarterectomy or surgical operation that is planned to occur during the course of the study.
8. Chronic atrial fibrillation (constant or paroxysmal), rheumatic valve disease, prosthetic heart valves or valve surgery
9. Any contraindications for ASA and/or clopidogrel treatment (also refer to the prescribing information of the concomitant medication)
10. The following conditions associated with increased risk of bleeding:
 - (a) History of intracranial, intraocular, spinal, retroperitoneal or atraumatic intra-articular bleeding

- (b) Gastrointestinal bleeding within the 12 months prior to Visit 2
 - (c) Gastric or duodenal ulcer disease verified by endoscopy or barium meal-double contrast technique within the 3 months prior to Visit 2
 - (d) Uncontrolled hypertension: systolic 180 mm Hg and higher or diastolic 100 mm Hg and higher (with or without anti-hypertensive treatment) as measured at Visits 1 and 2
 - (e) Hemorrhagic disorder
 - (f) Required concomitant therapy with nonselective NSAIDs
 - (g) Major surgical procedure or trauma within the 30 days prior to Visit 2.
11. Increased risk of bradycardic events (e.g. no pacemaker with known sick sinus syndrome, second degree A-V block, third degree A-V block or previous documented syncope suspected to be due to bradycardia)
 12. Patient with renal failure requiring dialysis
 13. Platelet count less than $10 \times 10^4/\mu\text{L}$
 14. Hemoglobin (Hb) level less than 10 g/dL
 15. Pregnancy or lactation
 16. Anticoagulant therapy within the 14 days prior to Visit 2.

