5.3 Procedures for handling subjects incorrectly enrolled or randomised

Subjects who fail to meet the inclusion criteria or who meet the exclusion criteria should not, under any circumstances, be enrolled or randomised. There can be no exceptions to this rule.

Where subjects that do not meet the selection criteria are randomised in error or incorrectly started on treatment, or where subjects subsequently fail to meet the study criteria post initiation, a discussion should occur between the AstraZeneca Study Delivery Team Physician and the Investigator regarding whether to continue or discontinue the subject from treatment.

The AstraZeneca Study Delivery Team Physician is to ensure all such decisions are appropriately documented. In situations where an agreement cannot be reached, the subject should have their study therapy stopped.

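### Section 5.6.3 accepts chronic daily non-selective NSAID use that exclusion 10(f) bars, and its sentence on other oral antiplatelets is at odds with the 14-day rule in exclusion 3

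*Protocol*

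**What the plan says.** Section 4.2 lists bleeding-risk conditions under exclusion 10. Item (f) is "Required concomitant therapy with nonselective NSAIDs". Section 4 says of the selection criteria: "Under no circumstances can there be exceptions to this rule". Section 5.3 repeats that patients "who meet the exclusion criteria should not, under any circumstances, be enrolled or randomised".

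Section 5.6.3 has a paragraph labelled Other oral antiplatelets. It covers other drugs with an antiplatelet effect, gives NSAIDs as the example, and says: "Treatment with these types of drug (including NSAIDs) is allowed pre-study and/or during the study". The choice is left to the investigator. It then warns that "chronic daily dosing with non-selective NSAIDs (eg, patient with rheumatoid arthritis) may increase the potential for GI bleeding", and continues: "so either alternative therapy or concomitant acid suppression is recommended". Selective COX-2 inhibitors are permitted with caution.

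Exclusion 3 in section 4.2 is "Concomitant antiplatelet therapy other than ASA within the 14 days prior to Visit 2". Section 5.6.3 repeats this 14-day interval for dipyridamole and cilostazol and bars them during the study. It does neither for other oral antiplatelets.

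**The concern.** Exclusion 10(f) and the chronic-use sentence in 5.6.3 describe the same kind of patient: one who needs a non-selective NSAID over the long term. The first bars that patient. The second tells the site how to manage the patient, and one of its two options leaves the NSAID in place. Every patient in this study takes ASA with either AZD6140 or clopidogrel, bleeding is singled out in secondary objectives 1 and 2, and 5.6.3 itself names the gastrointestinal bleeding risk. A site that reads only the concomitant-medication section could enter a patient whom the protocol regards as unsuitable.

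A second issue lies in the same sentence. Its grammatical subject is the whole class of other drugs with an antiplatelet effect, so it literally permits any oral antiplatelet not named in the preceding paragraphs. The primary variable is inhibition of platelet aggregation (IPA), which such a drug could affect directly.

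**Working it through.** The check is mainly a comparison of text.

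1. **Entry.** Take a patient with rheumatoid arthritis who needs a daily non-selective NSAID and cannot switch. Under 10(f) the patient is excluded, and sections 4 and 5.3 leave no room for judgement. Under 5.6.3, use before the study is allowed at the investigator's choice, and acid suppression satisfies the recommendation. The two instructions cannot both be followed.

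2. **What does not conflict.** 10(f) is limited to required therapy with non-selective agents. Occasional NSAID use, COX-2 inhibitors, and a chronic user who can be switched before entry all fall outside it. For these, 5.6.3 and 4.2 are compatible.

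3. **Need that arises on study.** 10(f) is an entry criterion and does not by itself forbid later use. Section 5.3 says that "where subjects subsequently fail to meet the study criteria post initiation, a discussion should occur" with the sponsor's physician, and that study therapy stops if no agreement is reached. Section 5.6.3 names only the investigator. This is a gap in alignment, not a contradiction.

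4. **How other excluded drugs are treated on study.**
   - Anticoagulants (exclusion 16): sections 5.6.1 and 5.6.2 forbid them and stop study drug if they become essential.
   - Fibrinolytics (exclusion 5): section 5.6.4 stops study drug if they are required.
   - Strong CYP3A inhibitors and inducers, and narrow-index substrates (exclusion 19): sections 5.6.6.1 and 5.6.6.2 forbid them and stop study drug if they are necessary.
   - Required non-selective NSAIDs (exclusion 10(f)): section 5.6.3 leaves them to the investigator.

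   The NSAID rule is the least strict of these.

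5. **Exclusion 3.** If NSAIDs counted as antiplatelet therapy there, any use in the 14 days before Visit 2 would exclude the patient and 10(f) would be largely redundant. The sensible reading is that 10(f) governs NSAIDs. That leaves oral antiplatelets other than NSAIDs that 5.6.3 does not name. Exclusion 3 bars them for 14 days before Visit 2, while 5.6.3 permits them before and during the study.

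6. **Size.** The documents give no frequency of NSAID use and no effect of NSAIDs or unnamed antiplatelets on IPA, so neither a number of affected patients nor an expected bias can be derived. A ceiling per patient can be. Section 11.5 truncates IPA to 0 to 100, and section 12.3 plans 34 Japanese patients per group with an SD of 25.
   - Planned precision: 1.96 × 25 × √(2/34) = 11.9, which reproduces the stated ±12.
   - Largest possible change in one arm's mean from one patient: 100/34 = 2.9 points.

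   The second figure is an arithmetic limit, not an estimate. A drug taken unchanged throughout is also present in the patient's own Visit 2 baseline.

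**The case against.** The strongest reply is that section 4.2 controls entry and is clear. Enrolling a patient who meets 10(f) is already a violation, whatever 5.6.3 says. The word required matters too: the first option in 5.6.3 is a switch, and a patient who can switch does not require the drug. The recommendation could also be read as addressing chronic use that starts after randomisation. The protocol writes on-study bans explicitly when it wants them, so discretion for NSAIDs may be deliberate. Other safeguards exist: exclusions 10(b), 10(c) and 17, stopping study drug after a major bleed (13.1.1), and DSMB review at least every 3 months (12.4).

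Much of this stands, and it limits the point. It does not remove the conflict, because 5.6.3 expressly includes use before the study and its acid-suppression option covers the patient who cannot switch. The safeguards do not tell a site which instruction to follow.

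A reader might infer three stronger claims that the documents do not support:
- That keeping a patient on study drug after a new chronic NSAID need breaches 10(f). It does not: 10(f) applies at entry, and 5.3 calls only for a discussion, with stopping if there is no agreement.
- That any NSAID use within 14 days of Visit 2 breaches exclusion 3. The separate and narrower 10(f) argues against that reading.
- That a material share of patients is affected or the primary comparison is seriously biased. The documents supply no figure for either, and any assumed prevalence would also have to assume that sites ignore 10(f).

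**Conclusion.** The concern holds in a limited form. Section 5.6.3 permits, with acid suppression, the chronic non-selective NSAID use that 10(f) bars at entry. Because 4.2 governs entry, the harm is conflicting site instructions on a bleeding-risk criterion in patients on ASA plus a P2Y12 inhibitor. On study, 5.6.3 is looser than the rules for the other excluded drugs, which is a weakness rather than a contradiction. The literal permission for unnamed oral antiplatelets is at odds with exclusion 3 and could affect IPA.

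The size cannot be estimated from the documents. The effect on the primary IPA estimate is likely small, on the assumptions that few such patients are entered and that their use is not concentrated in one dose arm. The case for a change rests on patient safety and clear instructions; it does not call for any added IPA analysis.

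**What to change.** Amend section 5.6.3 to state:

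1. Patients who require chronic daily non-selective NSAIDs are not eligible, with a cross-reference to exclusion 10(f). If the need arises during treatment, an alternative is used where possible; otherwise continuation is discussed with the sponsor's physician under section 5.3.
2. Oral antiplatelet drugs other than ASA and study drug are not allowed from 14 days before Visit 2 until the last PD sample.
3. Occasional NSAIDs and COX-2 inhibitors remain a matter for the investigator.

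The cost is a wording amendment. The downside is slightly narrower freedom in concomitant medication: an occasional patient may have to change pain treatment, or have continuation on study drug reviewed with the sponsor's physician.

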5.6.4 Fibrinolytic therapy

A patient is not eligible for inclusion into the study if fibrinolytic therapy has been given within 2 weeks prior to Visit 2 or is planned to be administered for any conditions during the study.

Clinical experience of fibrinolytics in combination with AZD6140 is not available at this time. If treatment with fibrinolytic therapy is required during the study, study medication must be discontinued.

5.6.5 P-glycoprotein interactions

AZD6140 and AR-C124910XX (active metabolite) are substrates and inhibitors of the p-glycoprotein transporter (also known as MDR1). In healthy volunteers mean trough digoxin (a

p-glycoprotein substrate) levels were increased about 30% with AZD6140 co-administration with maximum increases of about 3-fold. Levels of digoxin should be monitored closely following initiation of study medication and with any change in study medication. Other p-glycoprotein substrates may be expected to have similar changes in PK.

5.6.6 CYP3A interactions

5.6.6.1 CYP3A inhibitors

AZD6140 and AR-C124910XX (active metabolite) are metabolised by CYP3A. Therefore strong inhibitors of this enzyme (e.g. ketoconazole, itraconazole, voriconazole, telithromycin, clarithromycin, erythromycin, nefazadone, ritonavir, saquinavir, nelfinavir, indinavir, atazanavir or over 1 litre daily of grapefruit juice) are not permitted during the study as plasma levels of AZD6140 would be substantially increased (coadministration of AZD6140 with ketoconazole causes a 7.3-fold mean increase in area under the curve of AZD6140). If treatment with such therapies is necessary study medication dosing must be discontinued.

5.6.6.2 CYP3A substrates or inducers

Non-clinical data shows AZD6140 has different effects from activation through no effect to inhibition of CYP3A depending on the substrate studied. The *in vivo* effects of AZD6140 on the metabolism of the CYP3A substrates midazolam, simvastatin and atorvastatin have been examined.

In healthy volunteers midazolam levels were lowered by about 30% in the presence of AZD6140.

In healthy volunteer studies AZD6140 was found to increase simvastatin levels an average of about 50% with maximum individual increases of about 2- to 3 fold and increase atorvastatin levels an average of about 35%. As simvastatin has recommended restrictions for concomitant therapy with inhibitors of CYP3A due to increased reporting of myopathy, treatment with simvastatin or lovastatin (which is very similar pharmacokinetically to simvastatin) at doses higher than 40mg is not allowed during the study. There are no restrictions to other statin therapies as either they are not metabolised by CYP3A (pravastatin, rosuvastatin, fluvastatin) or have no restrictions for concomitant use with mild or moderate inhibitors of CYP3A (atorvastatin). Monitoring of patients for possible statin associated myopathy should be performed according to local practice.

The magnitude of these interactions would classify AZD6140 as a mild inhibitor or activator of CYP3A.

Treatment with CYP3A substrates with a narrow therapeutic index (e.g., cyclosporine, and quinidine) is not allowed during the study due to the observed changes with midazolam and simvastatin noted above. Treatment with CYP3A substrates with strong inducers of CYP3A also is not allowed during the study (e.g., phenytoin, rifampin/rifampicin, carbamazepine, phenobarbital). If treatment with such therapies is necessary study medication dosing must be discontinued.

5.6.7 Other medications

Other medication, which is considered necessary for the subject's safety and well being, may be given at the discretion of the investigator and recorded in the appropriate sections in the eCRF. Prescribing information of concomitant medication should be considered.

5.6.8 Treatment after study completion

After the patient has completed or discontinued the study they will be treated according to local medical practice. At Follow up Visit (Visit 6), the investigator will be free to decide what antiplatelet medication the patient should receive as part of his/her ongoing clinical care following the end of study treatment. This medication will be open label and obtained locally.

5.7 Treatment compliance

The administration of all study drugs (including investigational products) should be recorded in the appropriate sections in the eCRF.

The patient's compliance will be assessed by the investigator at each visit and recorded in the eCRF. Patients will be asked to return all unused investigational products and empty packages to the clinic. If the patient has taken study medication for more than 80% of the days between each visit the patient will be regarded as compliant.

5.7.1 Accountability

The study drug provided for this study will be used only as directed in the study protocol.

The study personnel will account for all study drugs dispensed to and returned from the subject.

For studies where study drugs are destroyed at site:

Study site personnel, if applicable, or the AZ monitor will account for all study drugs received at the site, unused study drugs and for appropriate destruction. Certificates of delivery, destruction should be signed.

For studies where study drugs are returned to AZ:

Study site personnel, if applicable, or the AZ monitor will account for all received study drugs and return all unused study drugs to AstraZeneca. Certificates of delivery and return should be signed.

For Japan, replace the above paragraph with the paragraph below

Study drug will not be distributed to the study site until the contract is concluded between the study site and AstraZeneca. The Investigational Product Storage Manager is responsible for managing the study drug from receipt by the institution until the return of all unused study drug to AstraZeneca. AstraZeneca will provide the study documents 'Procedures for drug accountability' and 'Procedures for drug storage' which describes the specific requirements. The investigator(s) is responsible for ensuring that the subject has returned all unused study drug.

5.8 Discontinuation of investigational product

Subjects may be discontinued from investigational product (IP) in the following situations:

- Voluntary discontinuation by the patient who is at any time free to discontinue his/her participation in the study, without prejudice to further treatment
- Safety reasons as judged by the investigator and/or AstraZeneca (e.g clinically significant ventricular pauses, syncope related to bradycardia, persistent increase in serum creatinine level of clinical relevance, persistent, unexplained anaemia (e.g. Hb <10 g/dL) or thrombocytopenia (e.g. platelet count <10 x10⁴/μL)
- Severe non-compliance to protocol as judged by the investigator and/or AstraZeneca
- Incorrect enrolment (ie, the patient does not meet the required inclusion/exclusion criteria) and the discontinuation is decided by the discussion (see Section 5.3)
- Pregnancy
- Development of a condition or an acute event (eg, MI or stroke) that necessitates treatment with one or more prohibited medications

Once randomised into the study all patients will be assessed until study closure unless informed consent is withdrawn for study participation.

Repeated attempts will be made to locate and determine the vital status and occurrence of any MI or stroke for those patients who are considered initially lost to follow up. A patient will be classified as lost to follow up only if, he/she has failed to return for the required study visits and his/her vital status remains unknown despite multiple attempts to contact him/her via telephone, fax, email, certified letter and through patient locator agencies (if allowed per national regulation).

5.8.1 Procedures for discontinuation of a subject from investigational product

A subject that decides to discontinue investigational product will always be asked about the reason(s) and the presence of any AEs. If possible, the subject should be seen and assessed by the investigator(s) at discontinuation visit and follow up visit as planned in [Table 1](#). AEs will be followed up (See Sections [6.4.3](#) and [6.4.4](#)), and all study drugs should be returned by the subject.

If a subject is withdrawn from study, see Section [5.9](#).

For Japan, replace the above paragraph with the paragraph below

A subject that discontinues will always be asked about the reason(s) for discontinuation and the presence of any AEs. The Principal Investigator/sub-investigator will perform the best possible observation(s), test(s) and evaluation(s) as well as give appropriate medication and all possible measures for the safety of the subject. They will also immediately inform AstraZeneca of the withdrawal. AEs will be followed up (See Sections [6.4.3](#) and [6.4.4](#)), and study drug should be returned by the subject.

